be regarded as treatment-emergent. For medications, the medication will be classified as concomitant.

- If the onset/start date is completely missing then the onset/start date will be imputed to the date of first dose of study treatment and therefore, for AEs, the event will be regarded as treatment-emergent and, for medications, the medication will be classified as concomitant.

The following rules will be applied to partial end/stop dates:

- If only the month and year are specified, then the last day of the month will be used;
- If only the year is specified, then December 31 of the known year will be used;
- If the stop date is completely unknown, the stop date will not be imputed.

Note that the start date or stop date of a prior medication (partial or otherwise) should not be imputed past the Screening date - 1.

In addition to onset and stop dates, the onset and end times of AEs occurring on the day of infusion will be collected on the eCRF. Onset and end times may also be recorded for other AEs that do not occur on the same day as the infusion. The duration of AEs with onset and end times will be calculated in days and hours:minutes (hh:mm) as:

$$\text{Duration of AE} = \text{End Date and Time} - \text{Onset date and time}$$

In cases where only the onset and stop dates are recorded for an AE, the duration of an AE will be calculated in days as:

$$\text{Duration of AE} = (\text{Stop Date} - \text{Onset Date}) + 1$$

Note that for participants who have an AE which starts and stops on the same day, but with only a start time or only a stop time recorded, it will be assumed that their AE started from 00:00 (if no start time is recorded) and ended at 23:59 (if no stop time is recorded) on that day.

If the date of a participant's initial diagnosis is incomplete, it will be imputed to the most recent feasible date for the calculation of time since initial diagnosis as follows:

- If only the day is missing, it will be imputed to the last day of the known month;
- If the day and month are missing, it will be imputed to December 31 in the known year;
- If the date of initial diagnosis is completely missing, then time since initial diagnosis will not be calculated.

The above date imputation rules will be applied to partially missing stop dates of a participant's last prior anti-cancer systemic therapy as well as partially and completely missing dates of progression/relapse on last prior anti-cancer systemic therapy.

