8.2 Adverse events

The primary safety endpoints for Part A of this study are the incidence and severity of TEAEs (including SAEs) from the first dose of study treatment on Day 1 of Cycle 1 until the end of the SFU Period (up to 30 days following the last dose of study treatment), and the incidence of DLTs from the first dose of study treatment on Day 1 of Cycle 1 until the end of the DLT Observation Period (Day 28 of Cycle 1).

All AEs in Part A of the study will be coded using MedDRA® and classified as pre-treatment and treatment-emergent relative to the first dose of study treatment. Adverse events with a start date prior to the first dose of study treatment will be defined as pre-treatment AEs. A TEAE is defined as any AE with a start date on or after the first dose of study treatment up until the last dose of study treatment + 30 days. A pre-treatment AE which increases in severity on or after the first dose of study treatment will also be counted as a TEAE. Note that in this case, the pre-existing AE will have a stop date and an outcome of 'worsened' and a new AE (with the same verbatim) will be entered with the same start date and the increased severity recorded on the eCRF. Any AE (including SAEs) with an onset date later than the last dose of study treatment + 30 days will not be considered as treatment-emergent and therefore will not be included in the tabulations of TEAEs. These AEs will be considered as post-study AEs and will be listed only. Where onset dates are missing or partially missing, AEs will be assumed to be treatment-emergent, unless there is clear evidence to suggest that the AE started prior to the first dose of study treatment and it has not increased in severity. Missing or partially missing dates for AEs

will be handled as described in [Section 4.2.3](#). All AEs for a participant will be recorded in the eCRF from the time of informed consent until completion or early discontinuation of Part A of this study. Serious adverse events are to be reported up to 30 days after the Final Visit (i.e. up to 150 days after the last dose of study treatment).

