In the overview summary of TEAEs, participants will be counted as having at least one TEAE with CTCAE severity grade ≥ 3 , and in the summary of TEAEs by maximum CTCAE severity grade, participants will be counted as having at least one TEAE in the following categories: ‘Grade 1’, ‘Grade 2’, ‘Grade 3’, ‘Grade 4’, ‘Grade 3 or 4’, ‘Grade 5’, ‘Grade ≥ 3 ’. Events for which no CTCAE severity grade is recorded by the investigator but an intensity is recorded instead, the intensity of this event will be assigned to a CTCAE severity grade for the purpose of these summaries, i.e. ‘Mild’ will be included as ‘Grade 1’, ‘Moderate’ will be included as ‘Grade 2’, ‘Severe’ will be included as ‘Grade 3’, ‘Life Threatening’ will be included as ‘Grade 4’ and, if the participant dies due to the event, it will be included as ‘Grade 5’. The determination of whether the event is life threatening or results in death will be based on the reason for seriousness recorded as life-threatening or death on the eCRF, or on the event having a fatal outcome. Otherwise, if both the CTCAE severity grade and intensity is missing then the CTCAE severity grade in these summaries will be missing. A study participant who experiences the same event multiple times will be included in the highest severity grade category in the summary of TEAEs by maximum CTCAE severity grade.

A glossary of all AEs will be presented including the MedDRA SOC, HLT, PT, reported term and low level term (LLT).

A listing of all AEs will be presented by study participant for the ES. The listing will include the onset date and stop date of the event (including relative days) and also the onset times and stop times of events where available. Period of onset of AEs will also be presented on this listing.

Period of onset of AEs will be defined as follows for the purpose of the listing:

- If the AE has an onset date prior to the date of the Screening visit, then Period=Pre-study;
- If the AE has an onset date on or after the date of the Screening visit and has an onset date and time prior to the start time of study treatment (i.e. prior to the start time of the infusion on Day 1 of Cycle 1) then Period=Screening;
- If the AE has an onset date and time on or after the start time of study treatment (i.e. on or after the start time of the infusion on Day 1 of Cycle 1) and up to the date and time of the start of Cycle 2 (i.e. prior to the start time of the infusion on Day 1 of Cycle 2) then Period=Cycle 1;

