- If the AE has an onset date and time on or after the start time of study treatment (i.e. on or after the start time of the infusion on Day 1 of Cycle 2) and up to the date and time of the start of Cycle 3 (i.e. prior to the start time of the infusion on Day 1 of Cycle 3) then Period=Cycle 2;
- Same as above for subsequent cycles (Cycle 3 etc.);
- If the AE has an onset date after the last dose of study treatment up to and including 30 days after the last dose of study treatment, then Period=SFU;
- If the event has an onset date after the 30-day period following the last dose of study treatment, then Period=Post-study.

The listing of all AEs will also include the AE duration (derived in days, hh:mm for AEs with onset and stop times recorded and derived in days for all other AEs with only onset dates and times recorded, days/time since infusion (time if an onset time is recorded, days otherwise), seriousness and reason for seriousness, CTCAE severity grade, intensity (where a CTCAE severity grade is not recorded), pattern of event, relationship to study treatment and action taken with study treatment (including other action taken), whether an autopsy was performed and cause of death. In addition, the listing will flag AEs that led to discontinuation from the study, TEAEs, AESIs, SAEs, infusion-related reactions, and DLTs. Whether an AE is related to a concomitant medication (which will include the COVID-19 vaccination), the names of any co-suspect medications and the outcome (sequelae, date and time) of the AE will also be listed.

Separate listings of all SAEs, TEAEs leading to discontinuation of study treatment and TEAEs leading to discontinuation of the study will also be presented.

All deaths that occur on study (defined as during study treatment or within 30 days of study treatment discontinuation) will be listed separately. This listing will include the primary cause of death and the number of days between the date of the last dose of study treatment and death.

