8.2 Adverse events

The primary safety endpoints for Part A1 of this study are the incidence and severity of TEAEs (including SAEs) from the first dose of UCB6114 treatment on Day 1 of Cycle 1 until the end of the SFU Period (up to 30 days following the last dose of UCB6114), and the incidence of DLTs from the first dose of UCB6114 on Day 1 of Cycle 1 until the end of the DLT Observation Period (Day 28 of Cycle 1).

All AEs for a participant will be recorded in the eCRF from the time of informed consent until completion or early discontinuation of Part A1 of this study. Serious adverse events are to be reported up to 30 days after the Final Visit (i.e. up to 150 days after the last dose of UCB6114). All AEs in Part A1 of the study will be coded using MedDRA® and classified as pre-treatment and treatment-emergent relative to the first infusion of UCB6114.

Adverse events with a start date prior to the first dose of UCB6114 will be defined as pre-treatment AEs. A TEAE is defined as any AE with a start date on or after the first dose of UCB6114 up until the last dose of UCB6114 + 30 days. A pre-treatment AE which increases in severity on or after the first dose of UCB6114 will also be counted as a TEAE. Note that in this case, the pre-existing AE will have a stop date and an outcome of 'worsened' and a new AE (with the same verbatim) will be entered with the same start date and the increased severity recorded on the eCRF. Any AE (including SAEs) with an onset date later than the last dose of UCB6114 + 30 days will not be considered as treatment-emergent and therefore will not be included in the tabulations of TEAEs. These AEs will be considered as post-study AEs and will be listed only. Where onset dates are missing or partially missing, AEs will be assumed to be treatment-emergent, unless there is clear evidence to suggest that the AE started prior to the first dose of UCB6114 and did not increase in severity. Missing or partially missing dates for AEs will be handled as described in [Section 4.4.1](#).

Adverse events will be assigned an NCI CTCAE severity grade (Grade 1/Grade 2/Grade 3/Grade 4/Grade 5), where possible. If a CTCAE toxicity grading is not possible, then the intensity of the AE (mild/moderate/severe) will be recorded on the eCRF. If the AE is not gradable, is serious, and is considered as life threatening, then the intensity for this AE will be missing and one of the reasons for seriousness will be recorded as life threatening.

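### The TEAE rule in both SAPs names only the start date, so an event timed before the first infusion on Cycle 1 Day 1 can be coded either way in the primary endpoint (minor)

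*SAP*

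**What the plan says.** Section 8.2 of the Part A SAP opens with the primary endpoint: "The primary safety endpoints for Part A of this study are the incidence and severity of TEAEs (including SAEs) from the first dose of study". Counting is thus meant to begin with dosing. Two rules then sort events by start date. One covers events before treatment: "Adverse events with a start date prior to the first dose of study treatment will be defined as pre-treatment AEs". The other covers treatment-emergent events: "A TEAE is defined as any AE with a start date on or after the first dose of study treatment". That window closes 30 days after the last dose. Section 8.2 of the Part A1 SAP repeats the pair: "A TEAE is defined as any AE with a start date on or after the first dose of UCB6114".

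The same section allows an exception where there is clear evidence of an earlier start, but only for onset dates that are missing or partial.

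Times are available. Section 4.2.3 of the Part A SAP says that "the onset and end times of AEs occurring on the day of infusion will be collected on the eCRF", and Section 4.4.1 of the Part A1 SAP says the same for UCB6114 infusions. Infusion start times are recorded too (Section 8.1 of each SAP).

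Later in Section 8.2 a further rule sets the onset period: "Period of onset of AEs will be defined as follows for the purpose of the listing". It does use time. An event on or after the Screening visit that "has an onset date and time prior to the start time of study treatment" is given Period=Screening, and Cycle 1 begins at the start of the infusion. Section 8.2 also says "the listing will flag AEs that led to discontinuation from the study, TEAEs, AESIs, SAEs, infusion-related reactions, and DLTs", so the TEAE flag and the period label stand on the same row. The Part A1 SAP is built the same way.

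**The concern.** TEAE incidence and severity are the primary endpoint of both modules and are meant to count from the first dose. If status is decided by calendar date, an event documented as starting on the morning of Cycle 1 Day 1, before any drug was given, enters that count. The listing would then show it as a TEAE that began during Screening.

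The SAPs elsewhere treat the pre-dose part of that day as pre-treatment. Table 3-1 in each makes the predose Cycle 1 Day 1 value the Baseline for ECG, physical examination, vital signs, laboratory data and ECOG status. A finding could therefore be Baseline in those summaries and a TEAE in the adverse event tables.

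The cohorts are small, so a single event is visible in a percentage. The wording also does not settle whether date or time governs, so two programmers could derive different primary results from the same data.

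**Working it through.** The plan gives no figure to reproduce. The check applies both rules to test records and then sizes one affected participant.

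**Step 1: apply the rules.** The clock times are illustrative; the first infusion is assumed to start at 10:00 on Cycle 1 Day 1.

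| Recorded onset | TEAE, by date (Section 8.2, literal) | Period (Section 8.2, listing) | TEAE, by date and time |
|---|---|---|---|
| Day before, 22:00 | No | Screening | No |
| Day 1, 08:00 | **Yes** | **Screening** | No |
| Day 1, 11:00 | Yes | Cycle 1 | Yes |

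Only the second record is affected. Its relative time under Section 3.2.1 (onset time minus infusion start) is 08:00 − 10:00 = −120 minutes. The exception for clear evidence does not reach it, because its onset date is complete.

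**Step 2: size of one affected participant.** If a participant has no other TEAE of the same preferred term, the incidence of that term rises by 100/n percentage points:

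- Part A cohort of 3: 100/3 = 33.3
- Part A cohort of 6: 100/6 = 16.7
- Part A1 cohort of 8: 100/8 = 12.5
- All Part A participants, up to 42: 100/42 = 2.4

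The sizes come from Sections 2.3 and 2.4 of the Part A SAP (3 to 6 evaluable per cohort, up to 42 in all) and Section 2.3 of the Part A1 SAP (up to 8 per cohort). The table denominators are treated participants, so replaced participants would make n somewhat larger. Overall TEAE incidence moves by the same amount only if the event is that participant's sole TEAE.

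**Step 3: which outputs are exposed.**

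- All-causality TEAE tables: exposed, towards over-counting.
- Non-serious TEAEs above the 5% threshold for EudraCT: one such participant exceeds it in any cohort of these sizes, since even 12.5% is above 5%.
- DLTs: must be related to treatment, as assessed by the investigator, so a pre-dose event is unlikely to qualify.
- Infusion-related reactions: need onset within 24 hours after the infusion start, and medical review (Section 8.2.2). The residual route is Section 13.1, where Category B, C and D TEAEs are paired by start date alone. A pre-infusion event could be paired with a post-infusion one before review.

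**The case against.** **The rule can be read as time-based.** Section 8.2 refers to the first dose, not to its date, whereas the partial-date rules in Section 4.2.3 name the date explicitly. The Part A1 SAP adds that events are classified relative to the first infusion of UCB6114, and an 08:00 event is not after an infusion that starts at 10:00. This stands. It rules out calling the misclassification certain and leaves an ambiguity: the rule names the start date and never calls for the collected time.

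**The period rule is for the listing only.** This also stands. A reader might infer two competing TEAE definitions. The text supports only a mismatch between the TEAE flag and a listing label.

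**The case would be visible.** The listing shows onset times and time since infusion, so a negative value could be spotted. That helps a reader of the listing but does not correct the tables.

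**The event is not attributed to the drug.** A reader might infer that each such event is charged to UCB6114, or is graded and assessed for relationship only because it is a TEAE. Section 8.2 provides for grading and relationship for adverse events generally, and TEAEs are tabulated by relationship. Reclassifying the event changes neither.

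**Frequency is unknown.** The percentages are simply 1/n and describe any single event in a small cohort. Nothing in the SAPs shows that pre-dose procedures on Day 1 generate adverse events with onset in those hours.

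**Conclusion.** The point holds as a minor one, in both SAPs. Taken literally, the date rule counts a documented pre-infusion event on Cycle 1 Day 1 as treatment-emergent and lists it under Screening. Because a time-based reading is also open, the primary endpoint can be coded in two ways.

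The literal reading over-counts all-causality TEAEs: 33.3, 16.7 or 12.5 points for a preferred term in a cohort of 3, 6 or 8, per affected participant with no other TEAE of that term. This assumes a complete start date, a recorded onset time before the infusion and no later worsening. The number of such records cannot be estimated from the SAPs and is probably small.

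The documents do not support a stronger claim that DLT or infusion-reaction conclusions are biased. Those outputs depend on investigator assessment, onset after the infusion start or medical review, and are largely unaffected.

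**What to change.** Add one rule to Section 8.2 of each SAP for adverse events that start on the date of first dose:

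- Treatment-emergent if the recorded onset time is at or after the start of the first infusion, or if no onset time was recorded.
- Pre-treatment if the recorded onset time is before that start, unless the event worsens after the infusion begins; the existing worsening rule then applies.

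State that only recorded times count. Section 4.2.3 (Part A) and Section 4.4.1 (Part A1) assume a 00:00 start for some same-day events without a start time, in order to derive duration. If that value reached the new comparison, an untimed event would become pre-treatment. Give the period rule the same default, so that an untimed Day 1 event falls in Cycle 1 and agrees with its TEAE flag.

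The cost is a short insertion in each SAP, one condition in the ADaM derivation and the guard on imputed times. Since it touches a key endpoint, Section 1 of each SAP points to an amendment if made before database lock. Only events documented as starting before any drug was given, and not worsening, leave the TEAE tables. They remain in the listing of all adverse events.
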